Design features (clinical trial / retrospective study / case) sample size, determination of the number of centers, study duration, if any randomization method and its importance Blindness method and its importance, if any	This study was planned as a randomized controlled experimental study. Computer-assisted randomization will be used to create groups (https://www.randomizer.org/). To determine the sample size, power analysis was performed using the $G^*$ Power (v3. 1.9) program. The power of the study is expressed as 1- $\beta$ ( $\beta$ = probability of type II error), and in general, studies must have 80% power. According to Cohen's (1988) effect size coefficients; Assuming that the evaluations to be made between two independent groups would have a medium effect size (d = 0.5), it was determined that there should be at least 64 people in each group, according to the calculation made using the t test.
Address of the clinic, laboratory, other medical units and institutions, if any, from cases, processing of data/keeping records, evaluation criteria, quality control and quality assurance	No samples will be taken from the babies forming the sample group.
Statistical method to be applied	The data obtained in the study were compiled using SPSS (Statistical Package for Social Sciences ) for Windows 25.0 program. In evaluating the data; Descriptive statistical methods will be used for number, percentage, min-max, mean and standard deviation values.  The compliance of the obtained data with normal distribution will be tested. Compliance with normal distribution can be examined with the QQ Plot drawing (Chan, 2003:280-285). In addition, normal distribution of the data used depends on the skewness and kurtosis values being between ±3 (Shao, 2002).  In normally distributed data, when comparing quantitative data, independent t test will be applied for the difference between two independent groups, when comparing two dependent stages, dependent t test will be applied, and when comparing more than two dependent stages, analysis of variance in repeated measurements (MIX ANOVA) will be applied and in case of a difference, Bonferroni will be applied to determine the group that makes the difference. will be used. Chi square analysis will be used to test the relationship between categorical variables.

- Kuller, J. M. (2014). Update on newborn bathing \_ newborn oath baby Nursing Reviews, 14(4), 166-170.

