TR Istanbul University-Cerrahpaşa ID: İstanbul UCEdu

Statistical Analysis Plan: June 1, 2023 The effect of two different bathing methods on vital parameters and stress levels in preterm babies.

Clinical Trial Number: NCT06166485

BIOSTATISTICS PRELIMINARY ASSESSMENT

The thesis summary and research hypotheses of the thesis titled "The effect of bathing applied in two different orders on the stress level and physiological parameters in term babies" were examined in detail. For this purpose, mothers who applied to the gynecology clinic of Istanbul Şişli Hamidiye Etfal Training and Research Hospital, whose weight was between 2.5 and 4 kg, whose Apgar score was over 7 points, who did not have any health problems, who were healthy term babies, and who voluntarily agreed to participate in the study. and their children will be included. As a data collection tool;

- Personal information form,
- Processing time (time to get the bath done),
- Babies' calm down time,
- newborn stress scale,
- Physiological parameters (body temperature, pulse, respiration, O2 saturation) will be used.

Data from IBM SPSS Statistics Standard Concurrent User V 26 (IBM Corp. , Armonk , New York, USA) will be evaluated in the statistical package program. Descriptive statistics will be given as number of units (n), percentage (%), mean \pm standard deviation ($Mean\pm SD$), median (M), minimum (min) and maximum (max) values. Shapiro-Wilk normality test will be used to ensure that numerical variables comply with normal distribution. The appropriate hypothesis testing method planned to be used in the study was determined as "Mixed Pattern Variance Analysis" if parametric test assumptions were met. In cases where the parametric test assumptions regarding the relevant test are not met, whether there is a difference between the groups in terms of quantitative variables will be evaluated with the "Student t test" if the parametric test assumptions are met, and with the "Mann-Whitney test" if the parametric test assumptions are not met. In examining whether the quantitative variables change according to the pre-test and post-test measurement time, they will be examined with the "Paired t test" if the test assumptions are met, and with the "Wilcoxon test" if they are not met. In all hypothesis tests, the probability of Type I error will be taken as α =0.05 and a value of p<0.05 will be considered statistically significant.

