Mohamed et al. $(2018)^{**}$ in their study, they investigated whether bathing applied in two different orders in term babies had an effect on stress level and physiological parameters. Differences between and within groups were calculated for body temperature (°C), heart rate (beats/ min) and oxygen saturation (%). Minimal significant change was observed in the study While the average heart rate (beats/ min) was 145 ± 16.44 points in the training group as a result of the first measurements, it was found to be 138 ± 12.12 points in the last measurement. In the control group, the first measurement was 140 ± 14.22 points and the last measurement was 139 ± 10.88 points. As a result, it was determined that there should be 86 observations in the sample with a statistical power level of 80.4% and a significance level of 5% for the calculated (f=0.128)* effect size. Considering sample loss (10%) such as dropping out of the study, it will be sufficient to work with at least 94 patients. The study was planned to include 47 people in each group.

^{*} COHEN, J., "Statistical Power Analysis for the Behavioral Sciences (Revised ed.)", 1977.

F tests - ANOVA: Repeated measures , within-between interaction

Analysis: A priori : Compute required sample size

Input: Effect size f=0.1275153

> α err prob =0.05=0.80Power $(1-\beta \text{ err prob })$ Number of groups =2Number of measurements =4 corr among rap measures =0.5Nonsphericity correction ϵ =1

Output: Noncentrality parameter λ =11.1869844

Critical F=2.6404222

numerator df = 3.0000000

denominator df = 252 =86 Total sample size

Actual power =0.8044596

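### The 80.4% power stated for 86 babies does not follow from the heart rates the SAP quotes: the pooled single-occasion SD gives about 67% with four measurements (illustrative) or 53% with the two occasions quoted

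*SAP*

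**What the plan says.** The sample-size section of the SAP takes heart rate from an earlier study of the same comparison. For one arm it reports that "the average heart rate (beats/ min) was 145 ± 16.44 points in the training group as a result of the first measurements", falling to 138 ± 12.12 at the last. For the other, "In the control group, the first measurement was 140 ± 14.22 points and the last measurement was 139 ± 10.88 points". It then concludes that "it was determined that there should be 86 observations in the sample with a statistical power level of 80.4"%, at a 5% significance level, "for the calculated (f=0.128)* effect size". Adding 10% for loss gives 94 babies, 47 per group.

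The G*Power listing below that text names the test as "F tests - ANOVA: Repeated measures , within-between interaction". Its inputs are f = 0.1275153, two groups, four measurements, correlation 0.5 and nonsphericity correction 1. Its outputs are λ = 11.187, critical F = 2.640, df 3 and 252, N = 86 and power 0.8045.

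On the number of occasions, the SAP's methods paragraph refers to two: "In examining whether the quantitative variables change according to the pre-test and post-test measurement time". The Protocol's section on statistical method allows for more: "when comparing more than two dependent stages, analysis of variance in repeated measurements (MIX ANOVA) will be applied". Neither document gives a schedule of four measurements or means at four occasions.

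**The concern.** The SAP presents f as calculated from the quoted heart rates but does not show the calculation. Working forward from those four means and SDs gives a smaller f than the one entered. Power for an interaction test depends on f squared, so a drop from 0.128 to 0.110 matters. The number of measurements matters too, because it multiplies the noncentrality, and the value used (4) is not tied to any stated schedule.

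This figure is the SAP's justification for recruiting 86 to 94 babies. If it is not supported, a non-significant interaction could be read as evidence that bathing order makes no difference, on the strength of 80% power that the quoted data do not show.

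**Working it through.** **1. The SAP's own figure.** G*Power's default formula for this test is λ = f²·N·m/(1−ρ), with df (m−1) and (N−2)(m−1), where m is the number of measurements. With f = 0.1275153, N = 86, m = 4 and ρ = 0.5: λ = 0.1275153² × 86 × 4 / 0.5 = 11.187, critical F = 2.6404, df 3 and 252, power 0.8045. Every printed output is reproduced.

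**2. The interaction in the quoted means.** The changes are 138 − 145 = −7 and 139 − 140 = −1, a contrast of 6 beats/min. Each cell's interaction residual is ±6/4 = ±1.5. For example, 145 − 141.5 − 142.5 + 140.5 = 1.5.

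**3. The SD.** Pooled variance = (16.44² + 12.12² + 14.22² + 10.88²)/4 = 737.75/4 = 184.44, SD 13.58. The λ formula already credits the correlation through 1/(1−ρ), so f must use this single-occasion SD: f = 1.5/13.58 = 0.1105.

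**4. Power with f = 0.1105, ρ = 0.5.**

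| Measurements | λ at N=86 | Power, N=86 | Power, N=94 |
|---|---|---|---|
| 4 (quoted interaction carried to four occasions) | 8.39 | 67.0% | 71.4% |
| 2 (the occasions quoted) | 4.20 | 52.6% | 56.3% |

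A simulated mixed ANOVA at N=86 (20,000 runs, SD 13.58, ρ 0.5) gave 67.1% with group gaps of 5, 5, −1, −1 and 52.5% with gaps of 5, −1. A t test on change that keeps the separate first and last SDs (SD of change 13.85) gave 51.0% at N=86. Even the SAP's own f of 0.1275 gives only 64.7% with two measurements.

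**5. A possible origin of 0.1275153 (inference).** The entered value equals √(0.016/0.984), so it corresponds to an eta-squared of 0.016. The quoted cells lead there if the variance is taken as 184.44 × (1 + 0.5)/2 = 138.33: eta-squared = 2.25/(138.33 + 2.25) = 0.01601, which rounds to 0.016. But 138.33 is the variance of the mean of two measurements at ρ = 0.5, a between-group error term. Used in the interaction formula it implies an error mean square of 138.33 × 0.5 = 69.2, whereas the quoted SDs give 184.44 × 0.5 = 92.2.

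**6. Sensitivity at N=86, one input changed at a time.**

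| Input varied | 4 measurements | 2 measurements |
|---|---|---|
| SD: first occasion 15.37 to last occasion 11.52 | 55% to 82% | 43% to 67% |
| ρ: 0.3 to 0.7 (assumed range) | 51% to 89% | 40% to 74% |
| Each mean rounded by up to 0.5, so contrast 4 to 8 (assumption) | 33% to 91% | 27% to 77% |

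Reaching 80.4% at f = 0.1105 needs ρ of about 0.62 with four measurements or 0.74 with two. If the group gaps at the two unreported occasions lie between +5 and −1 beats/min (assumption), four-measurement power runs from 37% to 67%.

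**7. Detectable at 80% power, ρ = 0.5.** Four measurements: f = 0.127 (N=86) or 0.121 (N=94). Two measurements: f = 0.153 or 0.146. For two measurements the difference in change is 4·f·13.58, that is 4 × 0.1528 × 13.58 = 8.3 beats/min or 4 × 0.1460 × 13.58 = 7.9, against the 6 quoted.

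**8. The first-measurement gap.** Of the 6 beats/min contrast, 5 is the difference at the first measurement (145 against 140) and 1 is the difference at the last (138 against 139). If the first measurement is before the bath, which the SAP does not state, randomisation makes that gap zero in expectation.

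**The case against.** The power calculation itself contains no error: given f, the output is right. The SAP quotes only the first and last measurements but enters four, so f may have come from all four occasions of the earlier study, which cannot be checked here. The 67% is fragile for the same reason. Group gaps of 5, 6, −2 and −1 over four occasions would give f = 0.130 and 82%, and every four-measurement range in the sensitivity table contains 80.4%. The 53% replaces the design entered with a two-occasion one, although the Protocol allows for more than two stages and the SAP's pre-test/post-test wording belongs to its paired tests. The origin suggested for 0.1275153 is conjecture: with a residual of 1.5, any SD from about 11.58 to 11.95 rounds to the same eta-squared. Finally, the Protocol asks for at least 64 per group; at N=128, f = 0.1105 would give 85% with four measurements, or 70% with two.

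Much of this stands. It rules out calling any one percentage the corrected power, or saying the sponsor certainly used the wrong error term. It does not rescue the stated figure. The SAP offers the quoted heart rates as the basis for f, and neither document supplies four sets of means, a four-occasion schedule or another derivation. The Protocol's 64 per group is a separate conflict over sample size and does not bear on the power claimed at N=86.

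**Conclusion.** The concern holds: 80.4% at N=86 is not supported by the data the SAP cites for it. With the pooled single-occasion SD and the SAP's correlation of 0.5, f is 0.110 rather than 0.128. Power is 67% with four measurements, assuming the first-to-last interaction carries over to four occasions, and 53% with the two occasions quoted.

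The two-occasion result is the firmer one: no single change of SD choice, of correlation within 0.3 to 0.7, or of rounding brings it to 80.4%. With four occasions some choices do, but the SAP does not say which it made, so a reader cannot tell whether the trial has 80% power for its planned test. The four measurements are unexplained rather than contradicted. The point about the first-measurement gap is secondary and depends on that measurement being before the bath. Confidence in the size of the shortfall is medium, because two occasions' means and the source of the correlation are not given.

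**What to change.** Keep N as it is and rewrite the SAP's sample-size paragraph:

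- Show how f was obtained, using the single-occasion SD that matches the interaction noncentrality formula.
- State the number of measurement occasions and use it in the calculation, with all four sets of means if it is four.
- Give a source or a range for the correlation of 0.5.
- Replace 80.4% with the recomputed power at N=86 and N=94. Alternatively, state the interaction detectable at 80% power from step 7 of the working.
- Say whether the first measurement is before the bath. If it is, do not plan on the 145 against 140 gap.

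The cost is one recalculation and a rewritten paragraph. The drawback is a stated power that will probably be less favourable.

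### The protocol and the SAP state different sample sizes (at least 64 against 47 per group), and the SAP's 94 does not quite cover its own 10% loss

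*SAP*

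**What the plan says.** **Protocol, design features row of the working protocol table.** The calculation compares two independent groups by t test. It assumes that the comparison "would have a medium effect size (d = 0.5"), refers to 80% power, and concludes that "it was determined that there should be at least 64 people in each group". That makes 128 in total, a figure the protocol does not print. The row gives no alpha, no sidedness and no allowance for loss.

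**SAP, Biostatistics Preliminary Assessment.** The calculation is for the within-between interaction of a repeated-measures ANOVA: f = 0.1275153 (0.128 in the text), alpha 0.05, target power 0.80, 2 groups, 4 measurements, correlation 0.5 and nonsphericity correction 1. From this, "it was determined that there should be 86 observations in the sample". The printed output ends with "Actual power =0.8044596". The next step reads: "Considering sample loss (10%) such as dropping out of the study, it will be sufficient to work with at least 94 patients". Then: "The study was planned to include 47 people in each group". No formula is given for the loss step.

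Both documents carry the date June 1, 2023, and neither refers to the other's calculation.

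**The concern.** A trial needs one planned number. Here two documents of the same date give 94 and 128, from different tests and different effect sizes, with nothing to say which governs. Someone checking whether recruitment was complete, or writing the sample size paragraph of the report, could cite either. The two are not interchangeable, because 47 per group falls well below what the protocol calls its minimum.

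Within the SAP, the sentence that moves from 86 to 94 claims to allow for 10% loss, but 10% off 94 leaves fewer than 86. That matters much less. It is a stated allowance that its own number does not fully deliver, in a sentence likely to be copied into the report. The two points belong together because the loss allowance cannot be settled until the basis is chosen.

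**Working it through.** **1. Reproduce the SAP's 86.** Noncentral F with lambda = f² × N × m / (1 − rho), df1 = 3, df2 = 3 × (N − 2). With f = 0.1275153, N = 86, m = 4 and rho = 0.5:

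- lambda = 0.1275153² × 86 × 4 / 0.5 = 11.187
- critical F(3, 252) = 2.6404
- power = 0.8045

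All agree with the printed output.

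**2. Reproduce the protocol's 64 per group.** Noncentral t with noncentrality d × √(n/2) and 2n − 2 degrees of freedom. Two-sided alpha 0.05 is my assumption. With d = 0.5 and n = 64, power is 0.8015, so the protocol's figure also reproduces.

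**3. Put each total on the other basis, with no losses.**

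| Total | SAP basis (f = 0.1275153) | Protocol basis (t test, d = 0.5) |
|---|---|---|
| 94 (47 per group) | 84.2% | 66.9% |
| 128 (64 per group) | 94.1% | 80.1% |

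**4. The SAP's loss step.**

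- 94 × 0.90 = 84.6, below 86.
- 94 − 86 = 8 losses, and 8/94 = 8.5%. Nine losses (9/94 = 9.6%, still within 10% of the total) leave 85.
- Dividing by the retention rate: 86/0.90 = 95.6, so 96, or 48 per group. Check: 96 × 0.90 = 86.4.
- Adding 10%: 86 × 1.10 = 94.6, or 43 × 1.10 = 47.3 per arm. The SAP's 94 (47 per arm) follows only if these are rounded down.

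**5. What the shortfall costs on the SAP basis.** At N = 85, lambda = 11.057 and power is 0.7993 with f = 0.1275153. With the rounded f = 0.128 it is 0.8026. At 86 it was 0.8045.

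**6. The same loss applied to 128.** The protocol states no loss, so borrowing the SAP's 10% is an assumption. 128 × 0.90 = 115.2.

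- SAP basis: 91.3% at 115.
- Protocol basis: 75.7% at 115 (58 + 57) and 76.1% at 116 (58 + 58), so about 76%.
- To keep 64 per group after 10% loss: 64/0.90 = 71.1, so 72 per group, 144 in total.

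**The case against.** The strongest case against the loss point is that the SAP plans by arm. The required 86 is 43 per arm, and 43 × 1.10 = 47.3 is 47 by ordinary rounding. Ten percent of 47 is 4.7, so the most that can be lost per arm without exceeding 10% is four. Four losses in each arm leave 43 + 43 = 86, exactly the requirement. The nine-loss case needs more than 10% loss in at least one arm (5/47 = 10.6%). This stands. A reader might infer that 94 is short under every usual convention. The documents do not support that, because the SAP states neither a formula nor a rounding rule. What remains is that 94 falls short of 86/0.90 and that 10% off the pooled total goes below 86.

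It can also be said that one baby is immaterial. That stands too: the power change is about half a point, and with the f printed in the SAP's text the target is still met at 85. The slip should not be read as a power problem.

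Neither argument touches the conflict between 47 and 64 per group. One could reply that the two calculations answer different questions, a mean difference and a group-by-time interaction. That explains why the numbers differ, but the plan still has to say which one sets the trial's size.

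**Conclusion.** The main point holds: documents of the same date plan 94 and at least 128, on different bases, and are not reconciled. If the protocol's calculation governs, 47 per group has about 67% power before any loss, 13 points under the stated 80%. This rests on d = 0.5 and an assumed two-sided alpha of 0.05.

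The loss point holds only as a minor slip: 94 covers 8 losses (8.5%), and a 10% loss leaves about 85 with power of about 80%.

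Two stronger inferences are not supported:

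- **That the SAP's trial is underpowered.** On the SAP's own inputs, 94 gives 84.2% with no loss and stays within 0.1 point of target at 85. The 67% belongs to the protocol's test and effect size only.
- **That adopting 128 disposes of the loss question.** It does so on the SAP's inputs. On the protocol's basis, an assumed 10% loss takes power to about 76%.

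**What to change.** Reconcile the protocol's design features row with the SAP's sample size paragraph so that both state one total, one basis (test and effect size) and one loss allowance with its formula. Say whether the number is enrolled or analysed.

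- **If the SAP basis and 94 are kept,** reword the loss sentence along these lines: *94 enrolled (47 per group) allows for up to 8 losses (8.5%) while keeping 86; with 10% loss about 85 remain and power is about 80%.* Replace the protocol's 64 per group to match. If a full 10% allowance around 86 analysed is wanted instead, the enrolled total is 96 (48 per group).
- **If the protocol basis is kept,** state alpha, sidedness and the loss allowance explicitly, and replace the SAP's 47 per group. With 64 per group analysed and an assumed 10% loss, the enrolled total is 144 (72 per group).

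The cost is a short edit to each document. Rewording the SAP's sentence around 94 needs no extra babies; adopting 96, 128 or 144 would mean enrolling more than the SAP now plans.

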journal for Specialists in Pediatric Nursing, 23(1), e12202. -Ceylan, S. S. , & BOLIŞIK, B. (2017). Newborn Stress Scale Examination of Psychometric Properties. Acıbadem University Journal of Health Sciences, (2), 97-103. Relevant sources have been added to the bibliography file. So et al. in 2014, investigating the effect of trunk-to-head bathing on the body temperature, heart rate and oxygen saturation of newborns compared to traditional head-to-torso bathing, it was found that stable and healthy term newborns bathed from trunk to head had lower body temperature before bathing than those bathed from head to trunk. It has been determined that they return to their temperatures faster (So, HS et al. 2014). In 2014, by Edraki et al., 50 premature babies in the neonatal intensive care unit were divided into two groups, experimental and control, by random distribution method. The babies in the experimental group were washed with the swaddle bath method, and the babies in the control group were washed with the traditional bath method. Body temperature was measured 10 minutes before and 10 minutes after bathing. Babies' faces were filmed during bathing to record their cries. The average temperature loss in newborns bathed with swaddle baths was lower than those bathed with traditional bathing methods. It was found to be significantly less than in newborns. Additionally, it was observed that the duration of crying was Summary of findings from significantly less in the experimental group than in the control group. Considering the positive effect of swaddling on maintaining body studies conducted / supporting information for this study temperature and reducing stress, it was concluded that it can be used as a suitable bathing method in the NICU (Edraki, M. et al.). Mohamed et al. to compare the effect of trunk-to-head bathing with traditional head- to-trunk bathing on the body temperature, heart rate, and oxygen saturation of newborns, it was found that trunk-to-head bathing had positive effects on newborns' body temperature, heart rate, and oxygen saturation compared to traditional head-to-trunk bathing. ( Mohamed , SS A et al. 2018). The results of this limited number of studies are particularly healthy and at term. There are no consistent results regarding the order in which newborns should be bathed. This suggests that there is a need for welldesigned randomized controlled studies on this subject. Based on this

babies.

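### The SAP's 94 babies and 80.4% power are justified only for a four-reading heart-rate interaction; at 47 per arm, two-group comparisons fall short of the protocol's own 80% standard

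*SAP*

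**What the plan says.** The protocol has four directional hypotheses: stress level (H1), physiological parameters (H2), calm-down time (H3) and procedure time (H4). Neither document names a primary outcome.

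The SAP has one sample size calculation, headed "F tests - ANOVA: Repeated measures , within-between interaction", with "Effect size f=0.1275153", 2 groups, 4 measurements and a correlation of 0.5. The only outcome figures shown with it are heart-rate means and SDs from a cited study. It gives a total of 86 with 80.4% power, raised for 10% loss to 94 (47 per group), and concludes that "it will be sufficient to work with at least 94 patients".

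Among its data collection tools the SAP lists "Processing time (time to get the bath done" and, separately, the babies' calm-down time. No measurement schedule is given for either. On analysis it states: "The appropriate hypothesis testing method planned to be used in the study was determined as" a mixed-design analysis of variance. The Student t and Mann-Whitney tests for group differences follow in a sentence that opens with a condition about failed assumptions.

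The protocol's design row has a different calculation: "Assuming that the evaluations to be made between two independent groups would have a medium effect size (d = 0.5", which leads to at least 64 per group for a t test. The same row says that studies must in general have 80% power. The protocol's statistical methods row gives the independent t test to two independent groups, and keeps repeated-measures ANOVA for more than two dependent stages.

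**The concern.** The SAP says that the research hypotheses were examined and then gives one unqualified statement of sufficiency. With no primary outcome to narrow it, a reader may take 94 babies and 80.4% power to cover all four hypotheses. The calculation covers one parameter of one of them.

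A duration recorded once per baby has no time factor, so the sizing test cannot be applied to it and its power does not carry over. For H1, the SAP says the cited study asked whether "bathing applied in two different orders in term babies had an effect on stress level and physiological parameters". Its next sentence lists computed differences only for temperature, heart rate and oxygen saturation. The protocol's summary of the same study likewise names only "body temperature, heart rate, and oxygen saturation compared to traditional head-to-trunk bathing". No stress mean, SD or effect size is given.

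What is at stake is the reading of null results. If 47 per arm is used and H3 or H4 is not significant, the result could be taken as evidence of no difference, although the comparison had about one chance in three of missing the effect that the protocol itself assumes.

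**Working it through.** **1. The SAP's own figure.** Inputs from the SAP output: f = 0.1275153, N = 86, k = 2 groups, m = 4 measurements, ρ = 0.5, ε = 1, α = 0.05.

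- λ = f² × N × m × ε / (1 − ρ) = 0.1275153² × 86 × 4 / 0.5 = 11.187
- df1 = (k − 1)(m − 1) = 3; df2 = (N − k)(m − 1) = 84 × 3 = 252
- Critical F(3, 252) = 2.6404; noncentral F power = 0.8045

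This matches the printed output. The figure is right for the test it describes.

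**2. The same test with one value per baby.** With m = 1, df1 = (2 − 1)(1 − 1) = 0, so there is no interaction to test. The 80.4% cannot describe procedure time, or calm-down time if that is recorded once.

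**3. Two-group comparison at the protocol's yardstick.** Inputs: d = 0.5 (protocol), α = 0.05 (SAP), n = 64 per group (protocol), 47 per arm (SAP, no loss) and 43 per arm (the SAP's 86 / 2). Neither document states whether the t test is two-sided; two-sided is assumed here. Power comes from the noncentral t with df = 2n − 2 and noncentrality d√(n/2).

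| n per arm | df | noncentrality | power at d = 0.5 | d for 80% power |
|---|---|---|---|---|
| 64 | 126 | 0.5 × √32 = 2.83 | 80.1% | 0.50 |
| 47 | 92 | 0.5 × √23.5 = 2.42 | 66.9% | 0.58 |
| 43 | 84 | 0.5 × √21.5 = 2.32 | 63.0% | 0.61 |

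The first row reproduces the protocol's 64. The chance of missing d = 0.5 is 1 − 0.669 = 0.331 at 47 per arm and 1 − 0.630 = 0.370 at 43.

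**4. Sensitivity.** The hypotheses are directional, so a one-sided test might be argued. At d = 0.5 it gives 77.7% power with 47 per arm and 74.4% with 43, still below 80%. A one-sided calculation would need 51 per group, so the protocol's 64 corresponds to a two-sided test.

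The documents give no effect size for stress or for either duration. Over an assumed range of d, two-sided power at 47 per arm is 30% (d = 0.3), 48% (0.4), 67% (0.5), 82% (0.6) and 97% (0.8).

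**The case against.** The strongest reply is that two-group comparisons are already assigned and sized. The protocol gives them the independent t test and 64 per group, and the SAP also names the Student t and Mann-Whitney tests. This stands. A reader might infer from the SAP's mixed-ANOVA sentence that H3 and H4 have no usable test; the documents do not support that. What is wrong is narrower: the SAP's conditional wording is garbled and does not send single-value outcomes directly to the two-sample test.

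It also stands that the shortfall exists only if the SAP's 47 per arm governs. At 64 per arm, power at d = 0.5 is 80.1%. The point therefore overlaps the conflict between the two sample sizes. It is not only that conflict, because choosing either number would leave the SAP's statement of sufficiency without a stated scope.

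A reader might also infer that H1 cannot use the sizing test. It could, if stress is scored repeatedly, which the SAP's pre-test and post-test wording allows; what is missing is a stress effect size. Nor do the documents show that the cited study did not measure stress. They show only that no stress figures are reported here, and the rest cannot be settled without that source.

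Finally, the SAP introduces the heart-rate data as showing the smallest change, which suggests a cautious choice, and it nowhere says that each hypothesis has 80% power. Both are fair. But caution among the physiological parameters says nothing about stress or durations, and the sentence on sufficiency carries no limit.

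**Conclusion.** The concern holds as a question of scope; the SAP's calculation contains no error on this point. The 86, 94 and 80.4% apply to a four-measurement heart-rate interaction, which is part of H2. For two-group comparisons at the protocol's d = 0.5, the SAP's size gives 67% power at 47 per arm and 63% at 43, against the 80% that the protocol asks for. The difference detectable with 80% power is 0.58 SD and 0.61 SD.

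This rests on a two-sided t test at 0.05, on 47 per arm being the size used, and on one value per baby. The last is a sound inference for procedure time and a likely one for calm-down time, but it is not stated. H1 is affected in the same way only if stress is compared at a single reading.

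A reader might conclude that 94 babies are too few. The documents do not show that: a true difference of about 0.58 SD or more would be detected with 80% power by 47 analysed per arm.

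**What to change.** 1. In the SAP's sample size text, limit 86, 94 and 80.4% to the heart-rate interaction, and say that no stress or timing effect was used.
2. Reconcile 47 with 64 per group across the two documents. If 47 is kept, state that two-group comparisons (H3, H4, and H1 if stress is compared at one reading) have 67% power at d = 0.5 and reach 80% only for d of about 0.58 or more, or 63% and 0.61 at 43 per arm. Add that a null result there is not evidence of no difference.
3. In the SAP's methods text, reword the conditional sentence so that outcomes with one value per baby go directly to the two-sample test, reported as the arm difference with its 95% CI, consistent with the protocol. State how often calm-down time and the stress scale are recorded.
4. On the cited study, say only that no stress figures are given.

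Items 1, 3 and 4 cost wording only. Item 2 costs wording if 47 is kept. If 64 is adopted, the total rises to 128, or 128 / 0.9 = 142.2, hence 144 in equal groups, if the SAP's 10% loss is applied. If 47 is kept, the stated power becomes less favourable for H3 and H4, and for H1 only if stress is compared at one reading.
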